7.1 Acupuncture

Acupoints of bilateral Zhongliao (BL33), Huiyang (BL35), Shenshu (BL23), and Sanyinjiao (SP6), which will be located according to the WHO Standardized Acupuncture Points Location³⁷ will be used. Zhongliao (BL33) is located in the sacral region, the third posterior sacral foramen. Huiyang (BL35) is located in the buttock region, 0.5 proportional bone (skeletal) cun (B-cun) lateral to the extremity of the coccyx. Shenshu (BL23) is located in the lumbar region, at the same level as the inferior border of the spinous process of the second lumbar vertebra (L2), 1.5 B-cun lateral to the posterior median line. Sanyinjiao (SP6) is located on the tibial aspect of the leg, posterior to the medial border of the tibia, 3 B-cun superiors to the prominence of the medial malleolus.

With patients in a prone position in relaxation, acupuncturists will use 75% alcohol pads to sterilize the skin around the acupuncture points and then insert Hwato-brand disposable acupuncture needles (sizes 0.30×75 and 0.30×40 mm) into the acupuncture points. For bilateral Zhongliao (BL33), the needle will be inserted approximately 50–60 mm with a 30° – 45° angle in an inferomedial direction. For Huiyang (BL35), the needle will be inserted approximately 50–60 mm in a slightly superolateral direction. For Shenshu (BL23) and Sanyinjiao (SP6), the needles will be inserted vertically with a depth of 25–30 mm. For acupuncture at BL23, BL35 and SP6, needle insertion will be followed by acupuncture manipulation of lifting and thrusting combined with twirling and rotating to reach *deqi*, which is defined as the sensation of aches, soreness, swelling, heaviness or numbness in the needle location region³⁸. Manipulations will be performed once every 10 minutes, 30 seconds each time. Immediately after needle removal, the acupuncturist will gently press the needled skin area with dry sterilized cotton balls to avoid bleeding.

7.2 Sham Acupuncture

The participants in the sham acupuncture group will receive minimally invasive, superficial needle insertion of 2–3 mm at bilateral sham BL23, BL33, BL35 and SP6 (non-acupuncture points lateral to the corresponding acupoints, 15 mm to BL23, BL33 and BL35; 10 mm to SP6). Treatment protocol will be similar to that of the acupuncture group, but Hwato-brand disposable acupuncture needles (size 0.30×25 mm) will be inserted at sham acupoints with depths of 2–3 mm without manipulation³⁹.

7.3 Standardization of Treatment

Guang'anmen Hospital will supply single-use, sterile, and disposable acupuncture needles for each participating site.

Two certified acupuncturists will be needed in each site to perform all the treatments, while the 20 sessions of treatment for each participant should be completed by one specific acupuncturist. All acupuncturists in this trial are required to have completed their professional training in acupuncture in universities of Chinese medicine with more than 2 years clinical experience.

To improve the consistency of treatments, acupuncturists at each site will receive trial-specific

(standardized operation procedure) training at the project launching session. The training will include detailed acupuncture points locations and manipulation methods in both the acupuncture and sham acupuncture groups. A video showing detailed information on how to perform the acupuncture and sham acupuncture will also be provided.

To avoid the inadvertent unblinding, acupuncturists will not tell anyone else the treatment allocation. The contacts between acupuncturists and participants should be as short as possible.

The acupuncturists will be instructed to follow standardized operating procedure:

Step 1:

The participant is piloted by research assistant to hospital bed, which was screened-off separately one-by-one. Their companions will be guided to wait outside the clinic, if any. The specific acupuncturist accepts the patient and asks the participant to take a rest. After a short while, acupuncturist instructs the patient to lie prone on the bed, with lumbosacral and lower shin areas exposed, and tell the participant that a 30-minute treatment will be given.

Before the first session of treatment, participants will be told that they may receive either the traditional acupuncture or sham acupuncture group, and they may not have sensation during the 30-minute retention of acupuncture needles out of body adaptation.

Step 2:

After sterilization, the acupuncturist will start to conduct administration according to treatment protocol. The acupuncture group will receive deep insertion of needles at acupuncture points, while the sham acupuncture group will receive superficial insertion of needles at non-acupuncture points.

Step 3:

After insertion of needles at appropriate areas, acupuncturist will conduct the first needle manipulation in the acupuncture group for 30 seconds, while in the sham acupuncture group, acupuncturists will hold the handles of acupuncture needles gently for 30 seconds without manipulations.

Step 4:

After 10 minutes, acupuncturist will conduct the second needle manipulation in the acupuncture group for 30 seconds, while in the sham acupuncture group, acupuncturists will hold the handles of acupuncture needles gently for 30 seconds without manipulations.

Step 5:

After another 10 minutes, acupuncturist will conduct the third needle manipulation in the acupuncture group for 30 seconds, while in the sham acupuncture group, acupuncturists will hold the handles of acupuncture needles gently for 30 seconds without manipulations.

Step 6:

After another 10 minutes, acupuncturist will remove the needles.

7.4 Permitted and Prohibited Concomitant Treatments

The use of medications or other therapies specific for symptoms of CP/CPPS will be discouraged during this trial, such as α blocker. However, medication use is allowed for intolerable symptoms as long as it is recorded accordingly, including the name and the dosage of the medication use. We will compare the proportion of subjects using rescue medications between groups.

8. Subject Evaluation

8.1. Outcomes Measurements

8.1.1 Primary Outcomes

The two co-primary outcomes include the proportions of responders at week 8 and week 32. The

responder is defined as a participant with a decline of 6 points or more from baseline in the total score of the Chinese version NIH-CPSI. As a validated, self-reported questionnaire, NIH-CPSI is widely used to assess CP/CPPS symptoms^{29,30}. NIH-CPSI consists of 9 items divided into 3 discrete domains: pain (0–21 points), urinary symptoms (0–10 points) and QoL (0–12 points), with a total score of 0–43 points (a higher score indicates worse symptoms). A decline of at least 6 points in NIH-CPSI has been identified as the minimal clinically important difference (MCID)²⁵.

8.1.2 Secondary Outcomes

Secondary outcomes include:

- (1) Proportion of responders during weeks 1-7, and at week 20.

The NIH-CPSI will be assessed once a week during treatment, and at week 20 and week 32. The responder is defined as who has a decline of 6 or more than 6-point from baseline measured by using the NIH-CPSI.

- (2) The change from baseline in NIH-CPSI total score during weeks 1-8, at week 20, and at week 32.
- (3) The change from baseline in NIH-CPSI subscales (pain, urinary symptoms and QoL) during weeks 1-8, at week 20, and at week 32.

- (4) The change from baseline in IPSS at week 4, week 8, week 20, and week 32.

IPSS is a valid, reliable and sensitive measure for patients with lower urinary tract symptoms (LUTS); it is widely used in clinical practice and research to determine the severity of LUTS, including incomplete bladder emptying, frequency of urination, intermittency, urgency, weak urine stream, straining and nocturia^{31,32}. Each of the questions is rated from 0 (not at all) to 5 (almost always); severity of LUTS can be graded as mild (0–7), moderate (8–19) or severe (20–35). IPSS will be assessed at the end of the 4th, 8th, 20th, and 32nd week.

- (5) The change from baseline in HADS at week 8, week 20, and week 32.

HADS will be assessed at the end of the week 8, week 20, and week 32. HADS is made up of 7 items for the assessment of depression and anxiety; the completion of this scale usually requires 2–5 minutes³³.

- (6) The change from baseline in IIEF-5 at week 8, week 20, and week 32.

Chinese version IIEF-5 will be assessed at the end of the week 8, week 20, and week 32. The IIEF-5 consists of 15 items in 5 domains with a total score ranging from 5 to 25 (mild ED, 12–21; moderate ED, 8–11; severe ED, 5–7); it is a psychometrically valid and reliable instrument with high sensitivity and specificity for detecting treatment effects in patients with ED of a broad spectrum of aetiology³⁴.

- (7) The change from baseline in EQ-5D-5L at week 8, week 20, and week 32.

The EQ-5D-5L will be assessed at the end of week 8, week 20, and week 32. The EQ-5D-5L is a generic instrument designed for self-completion and postal surveys; it is well-established and suitable for evaluation of QoL in participants with CP/CPPS³⁵.

- (8) The proportions of participants in each response category of the Global Response Assessment (GRA) at week 4, week 8, week 20, and week 32.

The proportions of participants in each response category of the GRA in the two groups after treatment will be measured at the end of the week 4, week 8, week 20, and week 32. GRA consists of 7 response categories: markedly worsened, moderately worsened, slightly worsened, no change, slightly improved, moderately improved, and markedly improved. We will identify a participant who reports “moderate” or “marked improvement” as a responder⁴⁰.

- (9) The change for peak and average urinary flow rate from baseline at weeks 8 and 32.

Peak and average urinary flow rates will be measured at weeks 8 and 32.

(10) Expectation assessment at baseline

Expectation assessment will be assessed at baseline, which includes two brief questions to investigate whether patients are confident that acupuncture treatment will help their CP/CPPS: “In general, is acupuncture effective for controlling the illness?”, “Do you think acupuncture will be helpful to improve your CP/CPPS symptoms?” For each question, participants could choose “Yes”, “No” or “Unclear” as the answer.

8.2 Evaluation Procedures

8.2.1 Schedule of Evaluation

	STUDY PERIOD											
	Enrolment	Allocation	Treatment								Follow-up	
TIMEPOINT (W, week)	-2 and -1	0	1	2	3	4	5	6	7	8	20	32
Enrolment												
Informed consent	x											
Eligibility criteria	x											
Demography characteristics	x											
Allocation		x										
Interventions												
Acupuncture			x	x	x	x	x	x	x	x		
Sham acupuncture			x	x	x	x	x	x	x	x		
Assessments												
Proportion of responders										x		x
NIH-CPSI	x		x	x	x	x	x	x	x	x	x	x
IPSS	x					x				x	x	x
IIEF-5	x									x	x	x
HADS	x									x	x	x
EQ-5D-5L	x									x	x	x
GRA						x				x	x	x
Expectation assessment	x											
Urinary flow rate	x								x		x	

Table 2. Enrolment, Intervention and Evaluation Schedules

Abbreviations: NIH-CPSI National Institutes of Health Chronic Prostatitis Symptom Index, IIEF-5 International Index of Erectile Function 5, HADS Hospital Anxiety and Depression Scale, GRA Global Response Assessment, EQ-5D-5L Five-level EuroQol five-dimensional questionnaire, VAS visual analogue scale

8.2.2 Baseline assessment

The baseline demographic information and outcome assessment will be collected in Visit 1 and Visit 2, which has been described in 5.2 Screening and Baseline Assessment.

8.2.3 Eight-week Treatment Phase

During the 8-week treatment (weeks 1-8), Visits 3-10 are scheduled weekly.

Participants will complete the NIH-CPSI every week; IPSS and GRA at weeks 4 and 8; and IIEF-5, HADS and EQ-5D-5L at week 8. We will provide a self-assessment questionnaires/scales notebook for each participant. They will be asked to complete the notebook at home weekly, and bring the manual to hospital the following week. Data from the notebook will be checked by outcome assessors, and then entered into the electronic database by CRC. Both the outcome assessors and CRC are unaware of the group allocation. The data from the notebook will be the raw data for analysis.

The urinary flow rate will be collected at week 8 after the treatment at hospital.

Within 5 minutes after treatment (sessions 19 or 20) at the week 8, the success of blinding will be assessed by outcome assessors at hospital.

8.2.4 Twenty-four-week Follow-up Phase

During the 24-week follow-up (weeks 9-32), Visit 11 will be scheduled at week 20, and Visit 32 will be scheduled at week 32.

Participants will complete the NIH-CPSI, IPSS, GRA, IIEF-5, HADS and EQ-5D-5L at weeks 20 and 32. Urinary flow rate will be completed at week 32.

For the results of Visit 11 (week 20), the notebook could be mailed to hospitals or submit to hospitals by participants in person. At weeks 32, participants need to visit the hospital in person for the examination of urinary flow rate, therefore they will bring the notebook to hospital by themselves.

9. Safety Assessment and Subject Withdrawal

9.2 Subject Withdrawals

Participants may withdraw from the trial at any time at their own discretion; the investigator may also determine whether it is in the best interest of subjects to withdraw from the trial due to worsening of symptoms, or the occurrence of a serious adverse event.

10. Administrative Responsibilities

10.1 Institutional Review Board

For every study site, only when the trial protocol is approved by the institutional review board, the enrollment of participant will begin, but all should be after July 25, 2017.

10.2 Funding

This study was supported and funded by the “the first batch of key research program in the 13th Five-year” (ZZ10-012) by the China Academy of Chinese Medical Sciences. The funder will not interfere the data collection, analysis, and interpretation; nor in the finishing of the manuscript, and decision to submit the manuscript for publication.

10.3 Compliance Improvement

- (1) Participants should participate in the trial voluntarily, and sign the informed consent;
- (2) Researchers assistants should record the participants' contact information in detail for the convenience of follow-up;
- (3) Before randomization, researchers should inform the participants that all the cost related to the examination and treatment would be exempted;
- (4) Each participant's participation in the trial should be taken charge of by the same research assistant and outcome assessor throughout the trial. They will explain the contents of notebook to participants if necessary, remind the participants of their schedule by phone or we-chat, and instruct participants to complete the notebook.
- (5) For participants who have less compliance, we will still follow them up to record outcome measurements through phone or message;

10.4 Data Management

10.4.1 The Raw Data Management and Archiving

We will use Remote Data Capture (RDC) system to perform data entry. The research assistants will fill out all the electrical CRF through RDC system. Researchers will inspect the eCRF, and signed electrically for the eCRF going into effect. The eCRF and the trace of eCRF revising will be left in the Oracle database.

10.4.2 Data Entry and Storage

10.4.2.1 Database Building and Testing, Data Entry Interface

The eCRF will be noted through CDISC SDTM standard, and the data entry interface will be generated through the Oracle Clinical software. The data entry interface should be in accordance with the paper version CRF as close as possible. The inputted data will be stored in the Oracle database. After preliminarily setting up the database, the entry clerks will input some analog data according to the CRF to test the database. The testing contains: (1) the agreement of the data entry interface and the paper version CRF; (2) the agreement of the exported data from the database and the analog data; (3) the agreement of the structure of the exported database and the paper-version CRF. After the testing, data administrators should revise the database and make a testing report. Then they electrically signed on the approval page of the database to indicate that the testing is completed. The electrical files of the analog CRF, Noted CRF, screenshot of the data entry interface, database testing report, and the approval page of the database should be saved. If the database updates during the trial, the electrical files mentioned above will also need to be updated.

10.4.2.2 Data Entry and Inspection

The research assistants take charge of the data entry for our trial. Before the entry, all the research assistants will accept the related training according to the data entry handbook. Researchers will inspect

the database, and then sign electronically to let the data go in to effect.

10.4.3 Data Verification and Problems Solving

Researchers will verify the data through Data Verification Plan (DVP) approved by the data administrator and the statisticians. Data queries will be inputted to a data query database, and form the DCF. After being inspected, the DCF will then be handed back to the original site, and the researchers of the site should answer the queries. Any revision of the database will be recorded through the RDC software.

10.4.4 Medical Coding

A data administrator who has the medical background will take charge of the medical coding. The contents of the coding are the clinical history, adverse events, and combined medication use if any. The clinical history and adverse events will be coded through MedDRA dictionary (Version 13.0), and the combined medication use will be coded via WHO DD dictionary (Version 2007.03). The lead researchers will verify the coded e-files.

10.4.5 Data Report

Data report contains the aspects as followed: (1) members of the project; (2) disagreement from the primary data management plan; (3) actual finish time of every project; (4) problems and solutions during data management (if have any); (5) reconstruction of the database (if have any); (6) distribution of the participants; (7) participants who disobey the trial protocol; (8) classifying plan of the statistical analysis population. Data report will be performed monthly since the first entry of the eCRF.

10.4.6 Data Auditing and Blinding Review

When the data checking is finished, a data auditing and blinding review meeting will be hold. In the meeting, the data administrators, statisticians, researchers, clinical inspectors, and other related members will have a discussion on the following items according to the data management report and the data lists:

- Distribution of the participants;
- Protocol disobeying or not;
- Possible outlier;
- Baseline data;
- Outcomes;
- Statistical analysis plan.

Participants will be classified to their suitable statistical analysis sets according to the definition in the protocol. No patient can be excluded from the analysis, unless getting the permission of the meeting participants. All the meeting participants will sign the data locking consent, and the data auditing resolution.

10.4.7 Database Locking

The database will be locked if it fulfills all the aspects as followed: All the queries have been solved, and the database has been updated; No query has been found through the data inspection; The medical coding has been completed; The plan of the participants' classification has been approved; The final draft of the SAP has been made, and approved by the project leader.

The statisticians and the data administrators will sign the data locking form, and then the database will be locked. The locked database will be sent to the statisticians for further statistical analysis through the data format of SAS.

10.5 Quality Control

(1) To guarantee the quality of the study, the trial protocol will be reviewed and may be revised by

expert acupuncturists, urologist, and statisticians several times.

- (2) A central randomization system will be adopted to avoid selection bias.
- (3) Strict eligible criteria will be pre-set to restrict the research population. The diagnosis, inclusion and exclusion criteria are designed in accordance with the guidance of NIH Chronic Prostatitis Clinical Research Network;
- (4) Trial-specific (standardized operation procedure) extensive training will be given to all the research staff participating the trial at the project launching session. Acupuncturists will be trained on how to use the central randomization system, the standardized manipulation method and needling rituals. Outcome assessors will be trained how to fill the case report form. Clinical Research Assistants (CRC) will be trained to use data entry system.
- (5) We will provide a self-assessment questionnaires/scales notebook for each participant. Participants will be asked to complete the notebook at home. During 8-week treatment period and the last assessment (Visit 12), participants will bring the notebook to hospital themselves. For the outcome assessment at week 20, they can mail the notebook to hospital or bring the manual to hospital themselves. The data from the notebook will be the raw data for analysis, and will be checked and recorded in CRF by outcome assessors. The data in CRF will be entered into the electronic database by CRC in a double-entry method. The statistical analysis of the data will be calculated by independent statisticians. The participants, outcome assessors, CRC and statisticians will all be unaware of the group allocation.
- (6) Participation processes in the trial of the same participants should be taken charge of by the same acupuncturist, research assistant and outcome assessor throughout the trial.

(7) A 3-level monitoring system will be established to periodically assess the performance of the trial: Level 1, Inspection; Level 2, Supervision; Level 3, Audit. Inspection: The investigator of each center will designate at least one researcher who take no part in the intervention to conduct a quality review of the center; Supervision: for each center, the study organizer (Guang'anmen Hospital, China Academy of Chinese Medical Sciences) will designate at least three researchers who take no part in the intervention to monitor the quality of the studies of that center; Audit: the China Academy of Chinese Medical Sciences will designate at least five quality control personnel to conduct a quality audit of the research.

11. Statistical consideration

11.1 Sample Size Calculations

Sample-size calculations were based on 90% power to detect a difference of 17% between response rates in the two groups (63.7% in the acupuncture group compared with 46.7% in the control group) for the primary outcome, defined as a decline of 6 or more points in the NIH-CPSI total score²¹. These values are equivalent to an odds ratio of 2.0. On the basis of a two-sided alpha level of 0.05, we calculated that a sample of 440 participants will be required (220 in each group). This proposed sample size includes a 15% increase to account for dropouts. To control for type I error, the two time points in the primary outcomes will have to be positive in order for the trial to prove the efficacy of acupuncture.

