6.1 Randomization

In this study, we will use permuted blocks randomization, stratified according to center. A web-response system of Central Randomization System for Clinical Research (designed by Clinical Evaluation Center, China Academy of Chinese Medical Sciences) will be applied in our trial. The allocation sequence will be generated by Institute of Basic Research in Clinical Medicine, China Academy of Chinese Medical Sciences using statistical analysis software SAS 9.4 with "proc plan" program. After production, the sequence will be signed and sealed by the staff who produce it and kept by other staff who take no part in this trial. It will not be allowed to be checked by anyone except the top system administrator.

Only acupuncturists in each center will have access to random numbers and group allocation prior to treatment through the web. Participants will be randomly assigned to the acupuncture or sham acupuncture group at 1:1 ratio.

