6.3.3 Analyses for Primary Outcome

Primary outcome analysis will be conducted with a logistic generalized linear mixed model (GLMM) for repeated measures. Responder or non-responder at each scheduled post-baseline visit (end of treatment, and 20 and 24 weeks after treatment) is the dependent variable. Subjects who discontinue without providing the NIH-CPSI score will be considered as non-responders. The logistic GLMM is fitted using the logit link and the binomial distribution. The model will include the baseline NIH-CPSI total score as a fixed-effect covariate, with treatment group (acupuncture and sham acupuncture), visit and treatment \times visit interaction as fixed-effect categorical factors. The interaction will remain in the model regardless of significance. Treatment group comparisons at each visit will be estimated by differences between least squares means from the treatment \times visit interaction, and will be presented as odds ratios with accompanying *p* values and 95% CIs. The predicted probability of response at each visit will also be presented. Such models provide fairly robust results for treatment comparisons when longitudinal binary responses are missing, with an assumption that data are missing at random(MAR), according to reported values³⁶.

Sensitivity Analyses for the Primary Outcome

Because the MAR assumption cannot be verified using the data, the sensitivity of inferences to departures from the MAR assumption should be tested³⁷. A straightforward sensitivity analysis for the MAR assumption in multiple imputation is based on the control-based pattern imputation model under the MNAR assumption by using the SAS procedure Proc MI process. Therefore, mixed-effect model under MNAR assumption will be used. 6.3.4 Analyses for Secondary Outcome

Efficacy analyses for all secondary outcomes will be performed in the ITT population, without imputation of missing data.

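### The 15% dropout allowance assumes dropouts leave the analysis, but the SAP keeps them as non-responders: at 15% missing, power per time point is about 84% rather than 90%, if the assumed rates are rates among men with data

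*Combined protocol and SAP*

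**What the plan says.** Protocol section 11.1 claims "90% power to detect a difference of 17% between response rates in the two groups", with assumed rates of "63.7% in the acupuncture group compared with 46.7% in the control group" taken from a cited earlier trial. It works "On the basis of a two-sided alpha level of 0.05" and arrives at 440 men, 220 per group. On dropouts it says only: "This proposed sample size includes a 15% increase to account for dropouts". It also requires a positive result at both primary time points, weeks 8 and 32.

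SAP section 6.2 bases every analysis on all randomised patients. SAP section 6.3.3 fits a logistic mixed model to responder status by visit and states: "Subjects who discontinue without providing the NIH-CPSI score will be considered as non-responders". The same paragraph then defends the model on the ground that it handles missing binary responses under a missing-at-random (MAR) assumption, and a control-based imputation follows as sensitivity analysis.

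Neither document adjusts the assumed response rates for men scored as non-responders.

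**The concern.** A dropout increase and non-responder scoring are two different ways of dealing with the same men. The increase works if dropouts leave the analysis and those who remain respond at the planned rates. Under non-responder scoring nobody leaves. Each dropout stays in the denominator with a fixed outcome, so both response rates, and the difference between them, are multiplied by the completion rate. The increase in numbers then offsets only part of the dilution.

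What is at stake is how a negative or split result will be read. A reader told that power was 90% would take a miss at week 32 as stronger evidence against a lasting effect than it is.

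**Working it through.** **Inputs.** From protocol 11.1: p1 = 0.637, p2 = 0.467, two-sided alpha 0.05, power 90%, 15% increase, 220 per group. From protocol 6.1: 1:1 allocation. From SAP 6.2 and 6.3.3: all randomised men analysed, discontinuation without a score counted as non-response. Not in the documents, so assumed: 15% without a score in each group at the visit analysed, and the correlation between the two tests. A two-proportion test stands in for the mixed model throughout.

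**Step 1: reproduce 440.** With mean rate 0.552,

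n = [1.960·√(2·0.552·0.448) + 1.2816·√(0.637·0.363 + 0.467·0.533)]² / 0.17² = (1.3784 + 0.8880)² / 0.0289 = 177.7, so 178 per group.

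Continuity correction: (177.7/4)·[1 + √(1 + 4/(177.7·0.17))]² = 189.3, so 190 per group.

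- Corrected: 190 × 1.15 = 218.5, so 219 per group (438 in total); 190 / 0.85 = 223.5, so 224 (448). Both are close to 440.
- Uncorrected: 178 × 1.15 gives 205 (410 in total); 178 / 0.85 gives 210 (420). Neither matches.

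The plan's figure therefore reproduces with the continuity-corrected formula.

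**Step 2: power if dropouts leave the analysis.** 220 × 0.85 = 187 per group at 63.7% versus 46.7% gives 89.6% corrected (91.4% uncorrected). On this reading the stated 90% is met, and multiplying by 1.15 instead of dividing by 0.85 makes little difference.

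**Step 3: power if dropouts count as non-responders.**

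- 0.637 × 0.85 = 0.541 and 0.467 × 0.85 = 0.397; difference 0.85 × 17.0 = 14.45 points; odds ratio 1.79.
- Mean rate 0.469. Standard error under the null √(2·0.469·0.531/220) = 0.0476; under the alternative 0.0471.
- Corrected: z = (0.1445 − 1/220 − 1.960·0.0476) / 0.0471 = 0.99, power 83.9%.
- Uncorrected (without 1/220): z = 1.09, power 86.2%. A simulation of the uncorrected test gave 86.1%.

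**Step 4: range over the proportion without a score (220 per group).**

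| Missing in each group | Rates | Power, corrected | Power, uncorrected |
|---|---|---|---|
| 5% | 60.5% vs 44.4% | 91% | 93% |
| 10% | 57.3% vs 42.0% | 88% | 90% |
| 15% | 54.1% vs 39.7% | 84% | 86% |
| 20% | 51.0% vs 37.4% | 80% | 82% |

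Power stays at 90% up to about 9% missing by the uncorrected formula, and up to between 6% and 7% by the corrected one.

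**Step 5: both weeks positive, 15% missing at each.** From a bivariate normal with equal power at the two visits:

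- Correlation 0.5 to 0.9: 74% to 80% corrected; 77.5% to 82% uncorrected.
- Correlation 0: 0.839² = 70% corrected; 0.862² = 74% uncorrected. This is a lower bound and not a plausible value. If the same 15% are non-responders at both visits, that alone induces a correlation of about 0.16: the covariance from shared dropout is 0.85·0.15·0.637² = 0.052 and 0.85·0.15·0.467² = 0.028 in the two groups, mean 0.040, against a mean variance of 0.244.

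**The case against.** Four objections deserve weight.

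*The meaning of 63.7% and 46.7%.* Section 11.1 does not say whether these rates already count dropouts as failures. If they do, there is no further dilution and 220 per group gives 94% power (95% uncorrected). This stands as a condition on the result. In that case, however, the 15% increase would have had no purpose, so 11.1 needs a clarifying sentence either way.

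*The missing-data rule.* Section 6.3.3 states non-responder scoring and a MAR rationale in one paragraph. If MAR governed men who discontinue, power would return to roughly the 90% of Step 2. The non-responder sentence is explicit, though, and it addresses the very men for whom the 15% was added; the MAR sentence describes a property of the model. I read the first as governing discontinuation, but the text should say so.

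*15% dropout is not 15% without a score.* The SAP rule applies only when the score is absent, and protocol 10.3 plans to follow less compliant men by phone or message. The 15% is an overall allowance, and missing scores may be fewer at week 8 than at week 32. This also stands, which is why the range in Step 4 matters more than any single figure.

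*The proxy.* A two-proportion test ignores the baseline covariate and the repeated measures. It does compare like with like, since the same kind of formula reproduces the plan's 440.

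A reader might infer that 440 is a miscalculation, or that the trial must be enlarged. The documents support neither. The figure reproduces, and the shortfall arises only when it is paired with the SAP's scoring rule. Holding 90% per time point at 15% missing would take 263 per group corrected (249 uncorrected), but a shortfall of this size can be dealt with by stating it.

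**Conclusion.** The concern holds conditionally. Sections 11.1 and 6.3.3 treat the same dropouts in incompatible ways. At the plan's own 15%, power per time point is about 84% on the formula behind the 440 (86% uncorrected), a loss of 4 to 6 points. Joint power for both weeks is about 74% to 80% corrected; part of that gap comes from the both-must-win rule and not from the dropout allowance.

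This rests on three assumptions that the documents leave open: the assumed rates are rates among men with data; the full 15% in each group lack a score at the visit analysed; and non-responder scoring, not MAR, governs discontinuation. It would therefore be too strong to say outright that 90% power is not delivered. At 5% missing it is, per time point.

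The issue is one of alignment between protocol and SAP. It is moderate in size and does not touch type I error.

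**What to change.** Keep 440 patients and change the text in this order:

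1. In SAP 6.3.3, state that the non-responder rule governs scores missing through discontinuation, and limit the MAR statement to other missing scores.
2. In protocol 11.1, state whether 63.7% and 46.7% already count dropouts as non-responders.
3. If they do not, restate 11.1 with the diluted rates and give the power that 220 per group delivers, per time point and for both together. Use one formula throughout (the continuity-corrected one matches the 440), show a range of dropout rates such as 5% to 20%, and name the correlation assumed for the joint figure.

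The cost is a few sentences and a less favourable stated power. No extra patients are needed, and conduct does not change.
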